C.3.2 Statistical analysis and sample size: We plan to enroll up to 30 older male subjects in a cross-over design (30 data points per treatment). Since this is an exploratory study, data obtained will be used to design future interventions that are larger in size and include women, and/or that more specifically investigate pathways that may be affected by acarbose. Data from this study will also be used to estimate effect size and to allow formal power calculations for future, larger studies. Previous studies of gene transcription have demonstrated that effect sizes on gene transcription can be substantial,³⁵ and differential expression can be detected in the same tissues, before and after an intervention in as few as 10-15 individuals.³⁶ Our study of resveratrol confirms the ability to detect differential expression in a sample size of 16, using a crossover design even when clinical effects are modest or negligible. Increasing the sample size to up to 30 will increase the ability to detect transcripts with a lower fold change.

RNA-Seq: Transcriptional profiles will be obtained by the use of the RNA-Seq assay at Einstein's Sequencing Core Facility, specifically using multiplexed 100bp single-end sequencing on an Illumina HiSeq2500. Under a separate protocol, #07-534, we have analyzed transcripts of muscle and adipose tissues obtained from unrelated young (20-30 yo) and we plan to submit another protocol to recruit additional young controls whose transcriptional profiles will further expand our "repository". These analyses will help us further define the parameters of biological transcript changes with aging. These results will provide "proof of concept" and help to set the stage for testing more interventions.

We anticipate $\sim 30M$ reads passing quality control to be aligned to the human genome. The alignment process will be implemented by use of the GSNAP and HTSeq packages – [version date 9/30/18]

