these specifically implement a splice-junction aware alignment protocol. Pair-wise correlation and principal component analyses on each sample's gene expression profile will be used to determine the quality of the experiment, identify batch effects and other systematics. Differential expression between samples (young and old, and after acarbose and after placebo) will be determined, using a negative binomial model approach such as that implemented in the DESeq package. Genes that show an adjusted p-value of less than 0.05 and a fold change greater than 2 will be selected for further scrutiny between placebo and acarbose conditions. Furthermore, our RNA-seq data will permit us to identify splice variants between the experimental conditions. The differential gene list will be processed with Ingenuity Pathway Analysis and GoStat, allowing us to identify dysregulated pathways and common gene ontology terms differentiating the acarbose transcriptome for the tissue types under scrutiny. Finally, the entire differential expression profile will be processed using the Broad's Gene Set Enrichment Analysis platform against over 10,000 curated gene lists, to provide additional regulatory perspectives on the data. These analyses are considered exploratory in nature and will be used to inform future tests that may target specific gene expression pathways. It will also allow us to make collaborative associations with phenotypes, although these associations will be complex considering the numerous potential age-delaying effects that may occur, some of which may be independent of the measured physiologic parameters.

Insulin sensitivity, biomarkers, etc.: Differences in mean acarbose vs. placebo treatment outcomes (insulin sensitivity, inflammatory biomarkers) will be tested for significance using paired t-test or Wilcoxon test (for non-parametric data). A two-tailed alpha level of 0.05 will denote statistical significance.

miRNA analysis:

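### The pathway analysis leaves the GSEA mode, the within-man pairing and the pathway threshold unstated, and the likeliest reading ignores correlation between genes and so inflates false pathways

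*Combined protocol and SAP*

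**What the plan says.** All of this is in the Combined protocol and SAP, section C.3.2, RNA-Seq paragraphs, unless another section is named.

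- **Design:** "We plan to enroll up to 30 older male subjects in a cross-over design (30 data points per treatment"), so each man gives one sample per tissue after each treatment.
- **Gene-level step:** the contrasts are given as "Differential expression between samples (young and old, and after acarbose and after placebo) will be determined". The method named for them is a count model: "using a negative binomial model approach such as that implemented in the DESeq package". No participant or period term is mentioned. Of the two contrasts, acarbose versus placebo is paired; young versus old compares independent groups.
- **Gene filter:** "Genes that show an adjusted p-value of less than 0.05 and a fold change greater than 2" are taken forward.
- **Over-representation step:** "The differential gene list will be processed with Ingenuity Pathway Analysis and GoStat".
- **GSEA step:** the input is described in the words "the entire differential expression profile will be processed using the", and the tool named for this is the Broad's "Gene Set Enrichment Analysis platform against over 10,000 curated gene lists".

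No ranking statistic, permutation type, set-size limits or p, q or FDR threshold is given for gene sets. Pairing is written in only for insulin sensitivity and biomarkers (paired t-test or Wilcoxon). The same section calls the expression analyses exploratory and says they will inform later tests that may target particular pathways. Specific Aim 1 is focused on ageing-related pathways, and section C.2.3 looks for ageing-specific pathways affected by acarbose.

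**The concern.** A differential expression profile is one number per gene. Once the data are in that form there are no sample labels left to permute, so the likeliest GSEA run is the ranked-list one, where the null comes from drawing random sets of genes. That null treats genes as independent. Genes in one pathway tend to move together between two biopsies whether or not the drug acts on them, so the pathway score varies more than the null allows. Over-representation tests on a gene list also take the gene as the sampling unit and share the assumption.

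Two things are at stake. Too many pathways would be called. The ordering would also be distorted, because the inflation grows with set size and correlation: large, tightly co-regulated sets rise up the list regardless of acarbose. The list is meant to inform later pathway-directed work, so its order matters even when no confirmatory claim is made.

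**Working it through.** The plan gives no GSEA error rate, effect size or pathway threshold, so there is no figure of its own to reproduce.

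**Inputs.** From the documents: 30 pairs and more than 10,000 gene lists. Assumed, because the documents give none: set size m, mean correlation between genes within a set (rho), within-man correlation of expression (ICC), and effect sizes. For a paired statistic the relevant rho is that of the within-man differences.

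**1. Closed form for gene permutation.** If genes are taken as independent, the variance of a set's mean score is understated by the factor VIF = 1 + (m - 1) × rho. The true error of a two-sided nominal 5% test is 2 × [1 - Phi(1.96 / sqrt(VIF))].

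Worked case: m = 100, rho = 0.05. VIF = 1 + 99 × 0.05 = 5.95; 1.96 / sqrt(5.95) = 0.80; error = 0.422.

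| m | rho 0.01 | rho 0.05 | rho 0.10 |
|---|---|---|---|
| 15 | 0.066 | 0.133 | 0.206 |
| 50 | 0.108 | 0.291 | 0.420 |
| 100 | 0.165 | 0.422 | 0.553 |
| 200 | 0.257 | 0.554 | 0.668 |

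At rho = 0 the error is 0.05 for every m, so correlation is the cause. Reading down a column shows the preference for large sets.

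**2. Simulation of the weighted running-sum GSEA score.** The closed form is for a set mean, so the GSEA score itself was simulated: 30 pairs, 60 sets of 50 genes (6 with a true shift), 60 replicates per scenario. Each scenario therefore has 60 × 54 = 3,240 null-set tests (standard error about 0.004 at 0.05).

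Gene permutation of a list ranked on a **paired** t:

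| Within-man rho | 0 | 0.02 | 0.05 | 0.10 | 0.15 |
|---|---|---|---|---|---|
| Error at nominal 0.05 | 0.050 | 0.146 | 0.25-0.26 | 0.352 | 0.431 |

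The inflation remains although the ranking statistic is paired, so it does not come from the crossover. As an illustration, 10,000 null sets of this kind would give 10,000 × 0.146 = 1,460 to 10,000 × 0.352 = 3,520 results below 0.05 (rho 0.02 to 0.10), against 500 expected. With Benjamini-Hochberg at 0.25, 62% to 84% of the sets called (pooled over replicates) were false whenever rho exceeded 0. Within-man label swapping gave 24% to 31% in the same scenarios.

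**3. Unpaired label permutation, same GSEA score** (compared with within-man swapping):

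| Gene correlations | Error, unpaired | Power, unpaired | Power, within-man swap |
|---|---|---|---|
| Within = between men (0, 0.05, 0.10) | 0.047-0.052 | 0.51-0.85 | 0.46-0.81 |
| Between 0.15, within 0.02 | 0.002-0.003 | 0.36-0.41 | 0.81-0.87 |
| Within 0.15, between 0.02 | 0.111 | 0.83 | 0.60 |
| Both 0.05, ICC varying by gene | 0.077 | 0.90 | 0.96 |

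In the last two rows the unpaired power is not comparable, because the error exceeds 5%.

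**4. Within-man swapping.** Its error was 0.040 to 0.047 in all eight scenarios.

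No error rate was computed for the Ingenuity and GoStat tests; for them the argument rests on the shared assumption.

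**The case against.** **The mode is not stated.** The profile may be called entire only to contrast it with the filtered gene list, and the run could still permute sample labels. This stands: gene permutation is the likeliest reading of the text, not a certain one. But the alternative is no safer as written, because the pairing is not carried into it.

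**The work is exploratory.** GSEA is included "against over 10,000 curated gene lists, to provide additional regulatory perspectives on the data", and the plan makes no confirmatory pathway claim. This limits the severity. It does not remove the point, because a distorted ordering is a poor basis for choosing what to test next, and an FDR threshold cannot repair p-values that are wrong to begin with.

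**Stronger readings that do not hold.** A reader might infer that the crossover itself makes the pathway p-values wrong. It does not: gene-permutation inflation would arise in a parallel trial too.

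A reader might also infer that unpaired label permutation must lose power. That is true of a plain difference in set means: at ICC 0.5 the error falls to 0.006, and 80% paired power falls to 51%. The GSEA score, however, is unchanged by a common rescaling of the ranking statistic, so the loss does not carry over automatically. The simulations show a neutral, conservative or anti-conservative test, depending on correlations that the documents do not give.

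Finally, the criticism about pairing does not reach young versus old, which is unpaired; the criticism of gene permutation does.

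**Conclusion.** The concern holds as an under-specification with a likely and material consequence, not as a demonstrated error. The plan fixes neither the GSEA mode, nor the handling of pairs, nor a pathway threshold. On the natural reading, the closed-form error at nominal 5% is about 7% to 67% for assumed correlations of 0.01 to 0.10 and sets of 15 to 200 genes. The simulated GSEA score gave 15% to 35% for 50-gene sets at 0.02 to 0.10. Any positive correlation examined produced inflation; its size depends on assumptions that the documents cannot settle.

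The count of false calls over 10,000 lists is only an illustration. It supposes that every list is null, has 50 genes with the assumed correlation, and is judged at raw p < 0.05, a rule the plan does not set for gene sets. For unpaired label permutation, the supportable statement is that its calibration is not assured in this design. The change should be made; the exploratory status keeps it below a critical defect.

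**What to change.** Add to section C.3.2, before the expression data are analysed:

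1. **Acarbose versus placebo.** Rank genes on a statistic from a model with participant, period and treatment terms. Take pathway p-values from one pre-named method that allows for both inter-gene correlation and pairing, and state the hypothesis tested. CAMERA, a correlation-adjusted competitive test, asks whether a set changes more than other genes. ROAST, or the GSEA score with labels swapped within man, is self-contained and asks whether the set changes at all. These are different questions, so the choice should follow the aim.
2. **Young versus old.** Use CAMERA or ordinary sample-label permutation. Within-man swapping does not apply here.
3. **Threshold.** Apply a stated FDR threshold to the pathway p-values, separately for muscle and adipose.
4. **Ingenuity and GoStat.** Report their p-values as descriptive.

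The cost is SAP wording, a different software call and a little extra analysis time, with no new data. Fewer pathways are likely to be called than under gene permutation.

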Visit 4: At the completion of the 10-week treatment period (up to 4 week titration, 6 week maximum dose) a standard mixed meal test (SMT) will be conducted and muscle and adipose tissue biopsies will be performed, after procedural risks are again explained by the physician performing the muscle and fat biopsies and a Montefiore procedural consent is signed by the participant. Fasting and 2hour blood samples will be collected for analyses noted above. Stool sample tubes will be collected. Vital signs and interval history will be obtained. Subjects will bring unused medication for assessment of adherence. Additional interim safety and/or adherence visits will be conducted if indicated. Instructions to maintain usual diet and activity patterns will be reinforced at each visit. Participants will be given treatment B, and will be instructed to start them after a 2-week washout. The same titration instructions detailed above will be provided to participants. Phone call- After a 2 week washout participants will be reminded to start treatment B with a phone call

Visits 5-6: The procedures in visits 3-4 will be repeated.

C.1.2 Inclusion and Exclusion Criteria:

[figure not shown]
Subjects with impaired glucose tolerance or with mild, untreated diabetes (defined below) based on a screening OGTT will be enrolled. Patients with a prior diagnosis of diabetes may enroll if they are not taking anti-diabetic medications and they meet OGTT criteria. If a participant has had an OGTT within the past year, results of this test may be used to determine eligibility. Given rodent studies demonstrating pronounced effects on males, we plan to recruit males for this small study, with a plan to study females in a subsequent, larger study if effects are seen. Although this approach decreases the generalizability of our initial findings, by increasing the homogeneity of the study population and targeting the gender most likely to benefit, we hope to improve the power to detect a treatment effect in this small, preliminary, study.

Inclusion:

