- **C.1.6 Assays:** The following assays will be performed in the core laboratories of the Einstein Institute for Clinical and Translational Research: chemistry and liver profiles, HbA1c and urinalysis, glucose, lipids, IGF-1, insulin, hs-CRP, adiponectin. 1mL of serum will be used for microRNA sequencing to be performed in the laboratory of [name]. Additional samples will be stored for future analysis of inflammatory markers, endothelial function, glycation end products, urinary F2 isoprostanes, FGF-21 and butyrate, or other markers of interest that may emerge.

C.2

Specific Aim 1: To assess the effect of acarbose on gene expression profile, with a focus on molecular pathways known or suspected to play a role in aging.

We hypothesize that treatment with acarbose will result in changes in the transcriptome in older adults. We will test this by identifying changes in gene expression in muscle and adipose tissue with RNA Sequencing (RNA-Seq). We may also study expression of specific target genes (using RT-PCR).

C.2.1 Detailed Methods

Muscle and adipose samples will be collected at baseline in all participants and at the end of each of the treatment period in older participants, in the fasting state following a 60-minute rest period. These procedures have been performed by our study group in IRB approved studies 2010-398 and 2014-3444.

Muscle Biopsy: A muscle sample of up to 200 mg will be obtained with a spring-loaded biopsy needle (Bard Instruments) in the mid-thigh region (vastus lateralis) following local anesthesia extending into the muscle area. The remainder of the ~ 100 mg muscle samples will be immediately homogenized in Trizol at the bedside, to inhibit any RNAase activity, frozen in liquid nitrogen and kept at -80°C, for subsequent rt-PCR, mRNA extraction and analysis of gene expression (RNA Seq) 31

The following assays will be performed on the samples: Skeletal muscle total RNA will be extracted using RNAeasy kit (Qiagen). cDNA will be made using SuperScript III First Strand (Invitrogen) and real time RT-PCR will be run using the LightCycler instrument (Roche). Five housekeeping genes will be used as controls. RNA-Seq assay will be performed at Einstein's Sequencing Core Facility, specifically using multiplexed 100bp single-end sequencing on an Illumina HiSeq2500. (http://www.illumina.com/technology/mrna_seq.ilmn).

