C.2.3 Specific Aim 2: To determine if treatment with acarbose will restore the gene expression profile of older, glucose intolerant men to that of young, healthy subjects. We hypothesize that transcriptional changes detected above may reflect some aspects of the transcription profiles of younger adults and provide insight into specific pathways affected by acarbose.

Under a separate protocol (2016-7110), young individuals aged 20-40 will be recruited and will undergo fat and muscle biopsies for RNA sequencing as detailed above. Changes

seen in the acarbose group in muscle and fat transcriptome will be compared to the young transcriptome, to identify aging-specific pathways affected by acarbose

C.3. Data analysis, rationale, limitations of experimental design:

C.3.1 Study design: We plan to conduct a double-blind placebo controlled trial with crossover design. The previous studies performed by our group (resveratrol and metformin) were cross-over studies with gene transcription data on 16 and 14 individuals, respectively. We identified clear differences in gene transcription profiles between resveratrol and placebo, using the same criteria outlined above. We expect that acarbose would have a similar if not larger effect size, thus 30 individuals in a crossover design is sufficient to detect differences. Data are still being analyzed for the metformin study. Cross-over study design is advantageous in terms of increased power for the study size. However, there is a risk for carryover effects since metabolic, transcriptional, and gut microbial changes may persist after the medication is cleared from circulation during the 2-week washout. Therefore, we plan to also separately analyze those who received treatment first in a sub-analysis to detect any long lasting changes that may result in a carry-over effect. Changes in physical activity and diet could confound interpretation of our metabolic studies, although the double-blind, placebo controlled study design will help to mitigate any potential impact. Changes in weight and body composition will also be carefully monitored. If there are significant changes in physical activity or weight, we will adjust for these in our data analysis.

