The circulating miRNA-seq raw files in the FASTQ format will be subjected to adapted trimming, alignment, normalization, removal of low abundance miRNAs and analysis using the SMiRK pipeline.³⁷ The trimmed files will be aligned with mature miRNA sequences in the latest version of mirBase database with read counts as the output, which will be normalized by rpm (reads per million) method, between libraries. With auto-elimination of miRNAs with <10 rpm, SMiRK will perform analysis on normalized data by arranging miRNAs as unsupervised hierarchical clusters. A Wilcoxon test will be used to compare miRNA expression levels. Differentially expressed miRNAs (p<0.05) will be validated with RT-PCR and Megaplex Pools protocol (Applied Biosystems). miRWalk database will be used to validate target gene expression.

Fecal microbiome 16s analysis:

The raw 16s sequence data will be converted to taxonomic profiles by grouping 16s sequences into Operational Taxonomic Units (OTUs) based on sequence similarity using an previously described protocol^{38, 39} as well as by generating de-novo OTU generation using *usearch*, a de novo OTU-picking tool (v6.0.307; http://www.drive5.com/). ^{40, 41} We will use Basic Local Alignment Search Tool (BLAST) to analyze each OTU's representative sequence against the most recent release of the Greengenes 16S database. ⁴² The microbial diversity among the treatment and placebo groups will be quantified and compressed into a single scalar statistic as previously described. ⁴³ Relative abundance plots will be

generated in QIIME for visual comparison of microbial abundances at each taxonomic level.

D: Potential risks of study participation

D.1.1. Potential adverse effects of Acarbose: Acarbose has been used extensively to treat diabetes internationally and has an excellent safety profile. The most common side effects are gastrointestinal, including diarrhea, flatulence and abdominal pain that result from the fermentation of unabsorbed carbohydrates and resultant gas production. In general, GI side effects develop within the first few days of therapy, are mild to moderate in severity, and decrease over time. There have been rare postmarketing reports of ileus and pneumatosis cystoides intestinalis associated with alpha-glucosidase inihibitors and use is contraindicated in the setting of colonic ulceration, colonic obstruction and in individuals at high risk for colonic obstruction.

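### The paired tests for insulin sensitivity and biomarkers omit the period effect, and analysing only the men given acarbose first cannot show whether carry-over occurred

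*Combined protocol and SAP*

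**What the plan says.** All references are to the combined protocol and SAP.

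- **Design and size.** C.1 and C.1.5 describe a randomised two-period crossover with 10 weeks per period and a 2-week washout. C.3.2 says "We plan to enroll up to 30 older male subjects in a cross-over design (30 data points per treatment". No sequence ratio or blocking is stated.
- **Clinical and biomarker outcomes (C.3.2, Insulin sensitivity, biomarkers, etc.).** Acarbose-placebo differences "will be tested for significance using paired t-test or Wilcoxon test (for non-parametric data", and "A two-tailed alpha level of 0.05 will denote statistical significance". The only adjustment mentioned anywhere is for changes in physical activity or weight (C.3.1).
- **Gene expression (C.3.2, RNA-Seq).** "Differential expression between samples (young and old, and after acarbose and after placebo) will be determined" with a negative binomial model. Subject and period terms are not mentioned.
- **miRNA (C.3.2, miRNA analysis).** "A Wilcoxon test will be used to compare miRNA expression levels". The form of the test is not given.
- **Carry-over (C.3.1).** The protocol accepts that metabolic, transcriptional and microbial changes may outlast the washout. Its response is: "we plan to also separately analyze those who received treatment first in a sub-analysis to detect any long lasting changes".
- **Sampling.** The schedule in C.1 places the meal test, biopsies, stored biomarker samples and stool at visits 4 and 6 only. The washout ends without a visit: "After a 2 week washout participants will be reminded to start treatment B with a phone call". C.2.1, however, states "Muscle and adipose samples will be collected at baseline in all participants", which the schedule does not show.

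**The concern.** Each man contributes one acarbose value and one placebo value, taken 12 weeks apart. Anything that moves outcomes between visits 4 and 6 (season, familiarity with the procedures, assay batch, ageing of the cohort) pushes the acarbose-placebo difference one way in men given acarbose first and the other way in men given placebo first. A paired test pools the two groups as if they shared one mean.

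The carry-over check raises a separate problem. It uses one sequence only, and one sequence yields one contrast. A small difference in those men could reflect a lasting acarbose effect, a weak acarbose effect or a period shift.

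A null or small result could therefore be misread. This matters beyond the study because C.3.2 says the data will supply effect sizes for the power calculations of larger trials.

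**Working it through.** **The plan's own figure.** Thirty men with one value per treatment give 30 values per treatment, as stated. The number 30 cannot be rebuilt from a power formula, because no effect size, SD or power is given. At two-sided 0.05, a paired t-test on 30 men has 80% power for an effect of 0.53 SDd, where SDd is the SD of the within-man difference.

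**Model.** Let τ be the treatment effect, π the common shift from visit 4 to visit 6, and λ the acarbose effect still present at the end of the placebo period. With d = acarbose − placebo:

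- acarbose first: E[d] = τ − π − λ
- placebo first: E[d] = τ + π

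None of τ, π, λ or SDd is in the documents. The values below are assumptions, in units of SDd.

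**Period effect, equal sequences (λ = 0).** The estimate is unbiased, but the expected sample variance of d becomes 1 + π² × n/(n − 1). With n = 30 and π = 0.5 this is 1 + 0.25 × 30/29 = 1.26, an SD of 1.12. The period-adjusted estimate is the average of the two sequence means, tested with the pooled within-sequence variance on n − 2 degrees of freedom. Simulation with τ = 0.5 and 15/15 completers gives:

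| π | Paired power | Adjusted power | Paired type I error |
|---|---|---|---|
| 0 or 0.1 | 75% | 75% | – |
| 0.25 | 73% | 75% | 4.4% |
| 0.5 | 67% | 75% | 2.9% |
| 1.0 | 44% | 75% | 0.6% |

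At π = 0.5 the signed-rank test has 65% power, against 74% for a rank-sum test on the period differences.

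**Period effect, unequal sequences.** The bias of the paired estimate is π × (number placebo first − number acarbose first)/n. At |π| = 0.5:

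- 13/12: 0.5 × 1/25 = 0.02, which is 4% of an effect of 0.5.
- 14/10: 0.5 × 4/24 = 0.083, which is 17% of the effect. Paired power is 41% or 70%, depending on the direction of the shift, against 64% adjusted. Paired type I error is 4.3–4.4%.
- 20/10: 0.5 × 10/30 = 0.167. With τ = 0.53 and the shift acting against acarbose, the paired estimate falls to 0.36. Paired type I error is about 10%.

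If randomisation were simple, the chance of exactly 15/15 is about 14%, and of 20/10 or worse about 10%. Averaged over simple randomisation, type I error stays at 5%, so the bias and the excess error are conditional on the split obtained.

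**Carry-over check.** Men given acarbose first supply τ − π − λ: one number for three unknowns. With π = 0, both (τ = 0.6, λ = 0.3) and (τ = 0.3, λ = 0) give 0.3. Comparing their mean d with that of the other sequence gives (τ − π − λ) − (τ + π) = −2π − λ, which still mixes period with carry-over.

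A baseline biopsy, if taken, would not resolve this. There is no outcome sample at the end of washout, and the change from baseline to the post-placebo value would combine carry-over with period and placebo effects.

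**Effect of carry-over on the estimate.** Even after period adjustment the estimate is [(τ − π − λ) + (τ + π)]/2 = τ − λ/2. If λ were half of τ, it would be 25% too small.

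The negative binomial model was not simulated, so these figures do not apply to RNA-Seq.

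**The case against.** The strongest points on the other side are these.

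1. **Size of the period shift.** A material loss needs π of about 0.5 SDd or more, and nothing in the documents suggests that. The plan also limits drift: usual diet and activity are reinforced at each visit, a standard meal is provided the night before the meal test, and weight or activity changes are to be adjusted for. This makes a large shift less likely, but none of these measures removes one.
2. **Time since acarbose.** In men given acarbose first, the placebo outcomes come 12 weeks after acarbose stops (2 of washout and 10 on placebo). Only an effect still present at week 22 counts as λ. This stands: λ equal to half of τ is a stress case. The protocol nonetheless raises persistence itself and offers this sub-analysis as its answer.
3. **Another reading of the sub-analysis.** It could mean a visit 4 comparison between sequences. That comparison is free of carry-over, but it does not show whether carry-over occurred.
4. **Scope.** The quantified outcomes are secondary in a study declared exploratory. For RNA-Seq the plan is silent rather than wrong, and principal components will be examined for batch effects and other systematic differences. This lowers the weight of the point. It does not justify keeping the weaker test where the plan names one.
5. **Weak replacements.** A 2×2 crossover of this size cannot detect modest carry-over by any method. This is correct, and the SAP should say so.

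**Conclusion.** The concern holds in both parts.

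**Period.** The stated paired tests ignore the period effect. With equal sequences they stay unbiased and are conservative; the loss is power: none at a shift of 0.1 SDd, 2 points at 0.25, 8 at 0.5 and 31 at 1.0, for an assumed effect of 0.5 SDd. With unequal completers the estimate is also biased, in either direction. Excess false positives were seen at 20/10; at 14/10 with a shift of 0.5 SDd there were none. Unequal completers are plausible, because no allocation ratio is fixed and men who cannot tolerate study medication are withdrawn.

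**Carry-over.** This conclusion needs no assumed values. Men given acarbose first, analysed alone, cannot separate carry-over from treatment or period, so the sub-analysis does not meet its stated purpose.

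The change should be made. The weight is moderate, since these are secondary outcomes of an exploratory study and the true period shift is unknown.

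**What to change.** - **Insulin sensitivity and biomarkers.** Use a mixed model with treatment, period and sequence as fixed effects and subject as random. Alternatively, compare within-man period differences between sequences with a two-sample t or rank-sum test.
- **miRNA.** Use the same rank-sum test on period differences.
- **RNA-Seq.** State subject, period and treatment terms in the negative binomial design.
- **Carry-over.** Replace the acarbose-first sub-analysis with (a) a visit 4 comparison of acarbose-first and placebo-first men, as a carry-over-free but imprecise sensitivity analysis, and (b) a descriptive comparison of placebo values at visit 6 (after acarbose) with those at visit 4 (before acarbose), labelled as period plus carry-over. Use neither as a pre-test. State that the design cannot rule out carry-over.
- **Baseline biopsy.** Reconcile C.2.1 with the visit schedule.

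**Cost.** SAP wording and standard code, with no new visits or samples. The period term uses one degree of freedom. If there is no period shift, it costs under 0.5 power points at 15/15, about 1.5 at 14/10, 1.6 at 13/9 and about 5 at 20/10.

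The carry-over analyses remain supportive only. With 15 per sequence and an effect of 0.5 SDd, the visit 4 comparison has about 35% to 13% power for within-man correlations of 0.3 to 0.8. A formal between-sequence carry-over test with λ half of τ has about 6–8%.
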